2.5.3 Summary of Venetoclax Nonclinical Pharmacokinetics

The pharmacokinetics of venetoclax was evaluated in mice, rats, monkeys, and dogs. Venetoclax pharmacokinetic (PK) profile was characterized by low plasma clearance and low to moderate volumes of distribution. Half-lives ranged from 2.2 hours in monkeys to 12 hours in dogs.

Venetoclax demonstrated high protein binding to human, rat, dog, and monkey plasma proteins (> 99.9%). Blood to plasma ratios showed that venetoclax does not partition preferentially into the red blood cells. Following oral administration of venetoclax to nonclinical species and humans, parent compound and metabolites were mainly cleared via biliary excretion and fecal elimination, with minimal renal clearance.

Venetoclax is predominantly metabolized by cytochrome P450 (CYP) 3A4 (CYP3A4) in vitro; UDP-glucuronosyltransferases (UGTs) are not involved in the metabolism of venetoclax. In addition, venetoclax is also a substrate for P-gp and BCRP. Active uptake of venetoclax was not observed in cells overexpressing OATP1B1, OATP1B3 or OCT1. In vitro studies indicated that venetoclax is not an inhibitor or inducer of CYP1A2, CYP2B6, CYP2C19, CYP2D6, or CYP3A4 at clinically relevant concentrations. Venetoclax is a weak inhibitor of CYP2C8, CYP2C9, and UGT1A1 in vitro, but it is not predicted to cause clinically relevant inhibition due to high plasma protein binding.

Venetoclax is a P-gp and BCRP inhibitor and weak OATP1B1 inhibitor in vitro. In vitro, venetoclax is metabolized by CYP3A4 and is a moderate inhibitor of CYP2C8. Definitive in vitro experiments showed that venetoclax is not predicted to be an inducer or inhibitor of the metabolism of CYP2C9 substrate compounds. Venetoclax is not a reversible inhibitor of CYP1A2, CYP2B6, CYP2D6, CYP2C19 or CYP3A4 ($IC_{50} > 30 \mu M$) in vitro and does not induce CYP3A4 or CYP1A2 at concentrations up to 10 μM .

2.5.4 Summary of Nonclinical Toxicology

Venetoclax has been assessed in repeated-dose general toxicology studies and in genetic, developmental/reproductive, and safety pharmacology studies. The primary toxicities associated with venetoclax administration included effects on the hematologic system (decreased lymphocytes and erythrocytes) in mice and dogs, the male dog reproductive system (testicular germ cell depletion), and embryo-fetal toxicity in mice.

2.5.5 Summary of Venetoclax Clinical Data

Clinical Efficacy Data for Venetoclax: Preliminary efficacy results are available for subjects with a variety of hematological neoplasms; venetoclax is approved for the treatment of CLL patients whose cells have a 17p chromosomal deletion and venetoclax in combination with rituximab is approved for the treatment of CLL or small lymphocytic lymphoma (SLL) patients, with or without 17p deletion, who have received at least one prior therapy.

- . Preliminary data indicate that venetoclax shows promising efficacy in AML.
- In Study M14-212 the ORR for subjects treated with venetoclax monotherapy was 19%.(43)
- In Study M14-358 the ORR for AML subjects (given venetoclax plus azacitidine or decitabine) was 68%.(44)
- In Study M14-387 the ORR for AML subjects (given venetoclax plus low dose ara-C) was 75%.(45)

Venetoclax Clinical Pharmacology and Pharmacokinetics: Venetoclax clinical pharmacology is being evaluated in several Phase I to III clinical trials, and data are available from three Phase I studies (M12-175, M13-367, M12-630), four Phase Ib studies (M13-365, M12-901, GO29440, GP28331), one Phase II study (M14-212) and five dedicated clinical pharmacology studies (Study M13-364, M14-497, M13-363, M14-253 and M15-101).

In the Phase 1 Study M14-358, preliminary pharmacokinetic results in 31 treatment-naïve AML subjects were available for venetoclax doses ranging from 400 mg to 800 mg when given in combination with decitabine (Arm A) or azacitidine (Arm B) and with or without posaconazole (Arm C). For Arm A and Arm B, venetoclax steady-state mean Cmax and AUC24 (Cycle 2 Day 5) ranged from 1.77 – 3.36 $\mu g/mL$ and 24.7 – 59.5 $\mu g/mL$, respectively. Based on the limited preliminary pharmacokinetic data, there was no evidence to suggest a marked effect of the co-administration of decitabine and azacitidine on the pharmacokinetics of venetoclax. In Arm C of this study, preliminary pharmacokinetic results from 6 subjects were available on Cycle 1 Day 20 (venetoclax 400 mg alone QD until Day 20) and Cycle 1 Day 28 (venetoclax 100 mg QD with posaconazole given from Day 21 to Day 28). Venetoclax Cmax and AUC following co-administration of venetoclax 100 mg with posaconazole were 2.1- and 2.7-fold higher respectively, compared to venetoclax 400 mg alone.

Preliminary pharmacokinetic results of venetoclax are available from 12 treatment-naïve subjects with AML in Cohorts 1 (600 mg) and 2 (800 mg) from the ongoing Phase 1 combination study of venetoclax and low dose cytarabine (Study M14-387). On Cycle 1 Day 10 (with cytarabine), venetoclax mean Cmax and AUC24 values ranged from 2.25 – 2.56 µg/mL and 34.7 – 44.6 µg•hr/mL, respectively. On Cycle 1 Day 18 (venetoclax alone), mean Cmax and AUC values of venetoclax ranged from 2.38 – 2.89 µg/mL and 37.9 – 45.3 µg•hr /mL. Dose-normalized Cmax and AUC24 of venetoclax on Cycle 1 Day 10 (with cytarabine) were comparable to dose normalized Cmax and AUC24 on Cycle 1 Day 18 (venetoclax alone), suggesting that co-administration of cytarabine did not markedly affect venetoclax exposures.

Clinical Safety Data for Venetoclax: As of 05 June 2017, three Phase 1/2 studies have been conducted in the AML indication as described below.

Overview of Phase 2 Study M14-212: Venetoclax Monotherapy in AML

This is a completed study with single agent venetoclax in subjects with R/R AML and those unfit for intensive therapy. A total of 32 subjects were dosed. Exposure, safety, and efficacy data are available for this study.⁽⁴³⁾ The most common adverse events observed in ≥ 30% of the subjects in Study M14-212 were nausea (59.4%); diarrhea (56.3%); hypokalemia, vomiting (40.6% each); fatigue, headache (34.4% each); hypomagnesemia (37.5%); febrile neutropenia (31.3%); abdominal pain, cough, hypophosphatemia (28.1% each); epistaxis, hyperphosphatemia, hypocalcemia, malignant neoplasm progression (25.0% each); dyspnea, hypotension, peripheral edema, pyrexia, and pneumonia (21.9% each). Serious adverse events were reported in 27 subjects (84.4%), the most common being febrile neutropenia (28.1%), malignant neoplasm progression (25.0%), and pneumonia (15.6%). Three serious adverse events were considered to have a reasonable possibility of being related to venetoclax (i.e., 1 event each of diarrhea, febrile neutropenia, and pseudomonal bacteremia). No cases of TLS occurred during venetoclax treatment.

In this phase II multicenter trial single agent VEN produced an overall response in 5/32 relapsed/refractory AML patients (CR in 1 patient, CRI in 4 patients) (46). Of the 5 patients with CR/CRI, 3 had *IDH* mutations suggesting that patients with *IDH* mutations may be particularly sensitive to VEN.

Two ongoing trials are evaluating VEN combination regimens in treatment naïve patients with AML who are ≥65 years of age and who are not eligible for standard induction: (a) to evaluate the efficacy and tolerability of the combination of VEN with a methyltransferase inhibitor (azacytidine or decitabine) (ClinicalTrials.gov Identifier: NCT02203773); (b) to evaluate VEN with low-dose cytarabine (ClinicalTrials.gov Identifier: NCT02287233).

Overview of Ongoing Phase 1b Study (M14-358): Venetoclax in Combination with HMA in Treatment Naïve AML

As of 09 March 2016, a total of 45 subjects ≥ 65 years of age with treatment naïve AML ineligible to receive standard induction therapy were enrolled into the escalation stage at 3 dose levels of venetoclax at 400 mg, 800 mg, and 1200 mg. Venetoclax was administered daily during the 28-day cycles in combination with decitabine (20 mg/m² intravenously on Days 1 – 5 once every 28 days) or azacitidine (75 mg/m² intravenously

or subcutaneously on Days 1 – 7 once every 28 days). Preliminary safety and efficacy data are available from the ongoing dose escalation stage of this trial.(45, 47)

The most common adverse events for all subjects in Study M14-358 were nausea (53.3%), diarrhea (44.4%), febrile neutropenia (40.0%), neutrophil count decreased (31.1%), platelet count decreased, cough, and fatigue (28.9% each), edema peripheral and hypokalemia (26.7% each). Events grade 3 and above were reported for the majority (91.1%) of subjects; the most common event was febrile neutropenia (40.0%). Serious adverse events were reported for 27 (60.0%) subjects, including febrile neutropenia (11 subjects), malignant neoplasm progression (3 subjects) atrial fibrillation, abdominal pain, non-cardiac chest pain, pyrexia, pneumonia, sepsis, bone pain (2 subjects each). All other events occurred in 1 subject each. The combination of venetoclax with decitabine and azacitidine demonstrates a tolerable safety profile.

As of 09 March 2016, the ORR, as assessed by the investigators for the subjects enrolled into the 3 dose levels, was 62.2% (28 of 45), with CR in 12 (26.7%), CRI in 15 (33.3%), and PR in 1 (2.2%). Four subjects (8.9%) were reported to have morphologic leukemia-free state (less than 5% blasts in bone marrow aspirate sample with at least 200 nucleated cells) after completion of Cycle 1. Eight patients (17.8%) had resistant disease. However, all of the patients with resistant disease had evidence of blast reduction at completion of Cycle 1. The patients enrolled into the 1200 mg dose level had a shorter follow-up at the time of this analysis.

The maximum tolerated dose has not been reached in either arm and dose escalation stage has completed enrollment. Enrollment into safety expansion at 400 mg and 800 mg dose of venetoclax in combination with both HMAs is ongoing.

Study M14-387: Study M14-387 titled, "A Phase 1/2 study of venetoclax in combination with low-dose cytarabine in treatment naïve subjects with acute myeloid leukemia who are ≥ 65 years of age and who are not eligible for standard anthracycline-based induction therapy," is an ongoing, open-label, multicenter safety and pharmacokinetics study. The primary objectives of the Phase 1 portion are to assess the safety profile, characterize pharmacokinetics, and determine the dose schedule, the MTD, and the RPTD of venetoclax in combination with low-dose cytarabine (LCD) in treatment-naïve AML subjects. The primary objectives of the Phase 2 portion of the study are to evaluate preliminary estimates of efficacy (including ORR and TTP) and to characterize the toxicities of the combination at RPTD. Secondary objectives of the Phase 2 portion include evaluating leukemia response (rates of CR, CRI, PR, RD, and HR including transfusion support needs) and DOR. An additional exploratory objective includes the evaluation of biomarkers that may serve as surrogate or predictors for clinical outcomes for future studies.

Of the 25 subjects in Study M14-387, 24 (96.0%) experienced at least 1 treatment-emergent adverse event. The most common adverse events for all subjects in Study M14-387 were: nausea (54%), febrile neutropenia (41%), diarrhea (44%), decreased appetite (33%), and peripheral edema (31%). Adverse events leading to study drug discontinuation occurred in 4 (16.0%) subjects, including 1 event each of disease progression, acute hepatic failure, Candida pneumonia, and subdural hemorrhage. Fatal adverse events occurred in 5 (20.0%) subjects: 2 events of malignant neoplasm progression and 1 event each of acute hepatic failure, Candida pneumonia, and lung infection.(44)

For further details of venetoclax preclinical studies, clinical studies, toxicities, pharmacokinetics, and adverse events please see the venetoclax Investigator Brochure (attached).

Experience with Venetoclax in combination therapy in relapsed and refractory myeloid malignancies

Efficacy of venetoclax combinations in the salvage setting will be presented at ASH 2017. Twenty-seven patients treated at our institution with relapsed/refractory AML (n=24), MDS (n=2) or BPDCN (n=1) received combinations including with decitabine (n=16) or azacitidine (n=5). Objective responses were achieved in 22% (n=6) of patients after a median of 1 cycle (range 1-4), including 11% with CRi and 11% with MFLS. 4 of the 6 responding patients received decitabine + venetoclax combinations, including 2 patients treated on the 5-day schedule and 2 patients treated on the 10-day schedule.

2.4 RATIONALE FOR STUDY

Second generation FLT3 inhibitors such as quizartinib and gilteritinib demonstrate potent anti-leukemic activity and improve outcomes in patients with relapsed/refractory AML with *FLT3-ITD* mutations(22). About 40-55% of FLT3-mutated patients not previously exposed to FLT3-inhibitors achieved marrow responses (CRc) to the second generation FLT3 inhibitors quizartinib(23-25) and gilteritinib(26), with 20-30% bridged to allogeneic stem cell transplant. Of note, recent FDA approval of midostaurin in combination with 7+3 induction chemotherapy in newly diagnosed FLT3-mutant AML signifies that essentially all relapsed FLT3-mutated AML patient will likely been exposed to at least one FLT3 targeting TKI. In this setting, the marrow response (CRc) rates with second generation FLT3 inhibitors such as crenolanib, gilteritinib and quizartinib have been reported to be lower than in prior FLT3 TKI naïve patients and are in the range of 20-25% (26, 48, 49) and Daiichi Sankyo unpublished communication).

Although response rates are high, the responses to single agent second generation *FLT3* inhibitors are almost invariably transient, maintained for 14-17 weeks, except among patients who undergo transplantation, due to the emergence of resistance(27, 28). The causes of resistance include the acquisition of point mutations in the *FLT3* KD (in 30-40% of resistant cases) and non-mutational mechanisms of resistance (in 50-60% of resistant cases) including up-regulation of compensatory pathways including the activation of anti-apoptotic proteins *BCL2*, *MCL1* and *BCL-x(L)*, *PI3K/Akt/mTOR*, *FOXO3A*, *SYK*, *RAS* and *STAT5/PIM* pathways, up-regulation of the *FLT3* ligand or receptor, mutations in other kinases (e.g. *CBL*), and tumor microenvironment mediated resistance(31).

[figure not shown]
MCL-1 was reported as an essential effector of *FLT3-ITD*-mediated drug resistance (50) and a number of *FLT3* inhibitors down-regulate *MCL1* thereby reducing the propensity to resistance to *BCL2* inhibitors. Combination of ABT-737 and *FLT3* inhibitors was synergistic in *FLT3-ITD*-mutated AML(51).

Furthermore, our recent data shows that *FLT3-ITD* activation/mutations may play a major role in primary and secondary resistance to ABT-199 (Popovic R, [name] et al, manuscript accepted to *American Journal of Hematology* May 2018). A phase 2 trial evaluated the efficacy and safety of venetoclax monotherapy in 32 patients with

relapsed/refractory acute myeloid leukemia (AML) or those unfit for intensive therapy(46). Venetoclax demonstrated activity and a tolerable safety profile in these patients with a CR/CRI in 6/32 (19%) of patients and biological activity defined as any measurable reduction in bone marrow blast counts after initiation of venetoclax therapy observed in 17/32 (53%) of patients. Occurrence of genetic mutations known to be associated with myeloid malignancies was investigated by next generation sequencing on blood and bone marrow specimens collected at baseline (32 patients) and relapse (20 patients). Eleven of 17 (65%) patients with biological activity had blasts containing mutations in the splicing factor genes *SRSF2/ZRSR2*, among them 6 patients also had blasts with mutations in *IDH1/IDH2*. Of the remaining 6 patients with biological activity, 1 patient had an *IDH2* mutation and the remaining 5 patients were wild-type for *SRSF2/ZRSR2/IDH1/IDH2*. Four of 15 patients (27%) without biological response to venetoclax had blasts with *FLT3-ITD* mutation prior to therapy. Four of the 17 patients (24%) with initial biological response to venetoclax acquired a new *FLT3-ITD* or *PTPN11* mutation at loss of response. Previous studies have shown that both these genetic alterations affect the expression of BCL-2 family members, suggesting that *FLT3-ITD* mutations may be responsible for primary and acquired resistance to venetoclax in AML patients by deregulating anti-apoptotic proteins. Furthermore, pretreatment and/or acquisition of *FLT3* mutations correlated with decreased time on study.

[figure not shown]
Based on our sequencing findings, we assessed the combination of venetoclax with the small-molecule *FLT3* inhibitor quizartinib in the *FLT3-ITD*⁺ mutant xenograft model MV-4-11. *In vitro*, the MV-4-11 cells were sensitive to BCL-2 inhibition by venetoclax.³ However, similar to our clinical observations, venetoclax did not inhibit the growth of these tumors when implanted *in vivo*. Although daily dosing of quizartinib induced tumor regressions in this model, the tumors eventually regrew. Strikingly, co-treatment with venetoclax and quizartinib induced similar tumor regressions as quizartinib alone but with significantly increased durability, preventing tumor re-emergence for up to 3 months post-cessation of treatment (Figure 1). These data suggested that combining venetoclax with *FLT3* inhibitors such as quizartinib could be highly effective for the treatment of *FLT3*-mutated AML (and potentially in non *FLT3*-mutated AML as well) and may also prevent the emergence of *FLT3*-mutated, venetoclax-resistant sub-clones in patients who do not have an already detectable *FLT3* mutation.

Figure 1: Tumor growth inhibition by venetoclax plus quizartinib in mice xenografted with *FLT3-ITD*⁺ MV-4-11 cells.

BCL-2 over-expression has also been implicated in maintaining the survival of FLT3-mutated AML cells. BCL-2 inhibition pre-clinically has been shown to potentiate the effects of FLT3-inhibitors, especially quizartinib (see attached prelim data from our lab) (Figure 2).

Figure 2: Venetoclax with FLT3-inhibitor in cell lines

Our collaborator [name] (Drug sensitivity testing for individualized therapies in hematologic malignancies. [name], OHSU Knight Cancer Institute, Portland, OR. AACR major symposium, 2016) has performed functional ex vivo screening of primary patient samples to identify effective small molecule drug combination strategies based on IC₅₀ evaluation. In his study the combination of quizartinib with venetoclax revealed a higher percentage of sensitive samples than to venetoclax alone or quizartinib alone. This was one of the most potent small molecule combinations of multiple evaluated TKI combinations

3.0 STUDY DESIGN:

3.1 General

The study will be a phase Ib/II, single-institution, open label, non-randomized, single arm, clinical trial. All patients will be registered through CORe/PDMS.

• Phase Ib

- This will include FLT3-ITD mutated patients with relapsed/refractory AML (up to four prior therapeutic regimens for AML i.e. up to salvage 4 status), including patients who may have been previously exposed to one prior FLT3-inhibitor other than quizartinib. Relapsed/ refractory status defined by the failure of at least one prior cycle of therapy for active AML (including but not limited to cytotoxic chemotherapy, hypomethylator therapy, immune-based therapy, stem cell transplant or stem cell therapy,

- one prior FLT3-inhibitor therapy exposure allowed, investigational therapy, and others).
- The DLT assessment period will be only during Cycle 1 of the Phase Ib (DLT assessment period = 28 days).

3.2 Study Design

- The phase Ib portion is aimed at finding the MTD and RP2D of the two drugs in this combination. The target dose is dose level +1, and the starting dose will be dose level 0. The first 6 patients on study will receive dose level 0.
- The Investigator is responsible for completing the cohort summary template and submitting to the IND office Medical Monitor for review and approval prior to advancing subjects to the next protocol specified cohort/dose level. A copy of the cohort summary should be placed in the Investigator's Regulatory Binder under "sponsor correspondence". This should be submitted after the first six patients.
- The dosing schema is shown in Table 1 below.

Table 1: Dosing schema

Dose level	Quizartinib	Venetoclax
+1 (Target dose)	60 mg daily	400 mg daily
0 (Starting dose, n=6)	30 mg daily	400 mg daily
-1	20 mg daily	400 mg daily

3.3 Dosing algorithm

The goal of the lead-in phase Ib is to determine the MTD and RP2D. We will first treat 6 patients at dose level 0 in the phase Ib. If DLT occurs in $\geq 2/6$ patients, this dose level would exceed the MTD, and 6 patients will be treated at the next lower dose level (i.e. dose level -1). If DLT occurs in $< 2/6$ patients at dose level 0, the next cohort of 6 patients will be treated at the next higher dose level (i.e. dose level +1). The dose escalation or de-escalation (Table 1) will continue in cohorts of 6 until we reach the highest dose level at which $< 2/6$ patients experience a DLT in the first 28 days. The highest dose level at which 0-1/6 patients experience a DLT in the first 28 days of treatment will be the MTD. The RP2D will be selected from among the doses evaluated after reviewing the efficacy, safety, pharmacodynamics data. The RP2D selected may be lower than the MTD. The RP2D will be used to treat an additional 20 patients in the phase II expansion portion of the study.

If $\geq 2/6$ patients experience DLT at dose level -1, the study may be revised to consider additional lower dose levels.

Patients that are removed from study before day 28 for any reason other than toxicity and have not experienced DLT will be replaced.

*With up to 1 potential dose escalation level (+1) to be studied and up to 6 patients to be treated at a given dose, the target maximum number of patients projected to be enrolled in the phase Ib part of the trial will be 12.

3.4 Definition of dose-limiting toxicity (DLT)

DLT is defined as a grade 3 or higher, clinically significant non-hematologic adverse event or abnormal laboratory value assessed as unrelated to disease progression, intercurrent illness, or concomitant medications and occurring during the first cycle on study, with the following exceptions:

- Grade 3 or 4 nausea, vomiting, or diarrhea that can be managed to ≤ grade 2 with standard antiemetic or antidiarrheal medications used at prescribed dose within 7 days of onset.
- Electrolyte abnormalities of Grade 3 or higher which can be corrected to grade 2 or less within 48 hours will not be considered as DLT only if the abnormalities are asymptomatic and corrected by optimal replacement therapy within 48 hours. Symptomatic grade 3 or higher electrolyte abnormalities will be considered DLT even if correctable within 48 hours.
- Grade 3 or 4 biochemical abnormalities of amylase or lipase without evidence of clinical pancreatitis.
- Grade 3 or 4 anorexia or fatigue.
- Grade 3 QTc prolongation will constitute DLT as follows: The QTc interval will be calculated by Fridericia's correction factor (QTcF). If the QTcF is > 500 msec the EKG must be evaluated within 4 hours in triplicate and if persistent ≥ grade 3 QTc prolongation is confirmed this will be considered a DLT. Note: Grade 4 QTc prolongation will be considered a DLT.
- All other clinically significant non-hematological adverse event that is Grade 3 according to the NCI CTCAE version 5.0 will be DLTs.
- Myelosuppression and cytopenias are expected outcomes of leukemia treatment and *per se* will not constitute DLT. Only prolonged myelosuppression, as defined by the NCI criteria specific for leukemia, i.e. marrow cellularity < 5% with grade 4 neutropenia or thrombocytopenia on Day 42 or later from start of therapy without any evidence of leukemia, will be considered in defining DLT. In case of a normocellular bone marrow with no evidence of leukemia, 8 weeks with grade 4 neutropenia or thrombocytopenia will be considered a DLT. Anemia will not be considered for the definition of DLT.

Any patients who stop treatment prior to completing evaluation for the DLT observation period (first 28 days) due to disease progression or refusal for further participation for reasons other than

toxicity during the DLT defining phase Ib portion of the study will be replaced for DLT evaluation. Patients who come off study earlier than 28 days during the DLT evaluation period may continue therapy off protocol if they are having clinical benefit, after discussion with the PI. The rationale for continuing therapy must be clearly documented in the patients chart.

Patients must receive at least 75% of the scheduled doses of quizartinib and at least 75% of the scheduled doses of venetoclax, respectively, in any given cohort to be eligible for DLT evaluation. Patients who receive <75% of the scheduled dose of either quizartinib or venetoclax will not be eligible for DLT evaluation and must be replaced. However, subjects who are unable to complete at least 75% of the prescribed dose of venetoclax and quizartinib in Cycle 1 (28 days) due to clinically significant non-hematologic adverse event or abnormal laboratory values that meet the definition of DLT in section 3.4 will be considered to have a DLT. Such patients may continue to receive protocol therapy if they are having clinical benefit, after discussion with the PI. The rationale for continuing therapy must be clearly documented in the patient's chart.

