5.1 Schedule

All patients will be registered through CORe.

The Phase Ib dose escalation stage of the study will evaluate the safety, tolerability, PD and PK of venetoclax in combination with quizartinib, with the objectives of identifying the MTD and RP2D for each combination.

Quizartinib will be administered orally daily continuously starting on cycle 1 day 1. Patients will self-administer quizartinib tablets orally QD. If a dose is missed or vomited, the next dose should not be increased to account for missing a dose. The subject should take the next regular dose at the regularly scheduled time. Patients will receive one cycle of therapy every 28 days (+/- 7 days). Cycle 1 Day 1 of each cycle will be counted from the start of the quizartinib dosing. Quizartinib dose escalation criteria will be maintained as suggested in quizartinib Investigational Brochure (IB) as follows:

1. If the target dose for the given patient in the phase IB or phase II portion is quizartinib 30mg the patient will start the dosing on C1D1 at quizartinib 30mg per day
2. If the target dose for the given patient in the phase IB or phase II portion is quizartinib 60mg the patient will start the dosing on C1D1 at quizartinib 30mg per day and can increase to quizartinib 60mg per day on C1D12 only if QTcF on triplicate ECG is <450 msec on the Day 12 post-dose EKG

The initiation of venetoclax will be deferred for 7 days in cycle 1 to allow clinical and correlative evaluation of quizartinib single agent activity, and to debulk tumor burden thereby reducing the risk of tumor lysis syndrome (TLS). The intent is to initiate venetoclax on cycle 1 day 8. Blood samples will be collected at pre-dose, 2 (+/- 30 minutes), 4 (+/- 30 minutes), 6(+/- 30 minutes), 8 (+/- 30 minutes) and 24 (+/- 30 minutes) hours post-dose on cycle 1 day 14 to measure venetoclax, quizartinib and AC886 concentrations in patients enrolled in the dose-escalation period (n=12). The WBC count must be <10K prior to the initiation of venetoclax dosing. Note: Hydroxyurea can be used if needed during these initial 7 days to control WBC count, if needed.

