It is suggested that each dose of venetoclax be taken with approximately 240 mL of water within 30 minutes after the completion of a low-fat breakfast. Examples of a low-fat breakfast include 2 slices of white toast with 1 tablespoon of low-fat margarine and 1 tablespoon of jam, and 8 ounces/240 mL of skim milk (319 calories and 8.2 g fat) or 1 cup/30 g of cereal, 8 ounces/240 mL of skim milk, 1 slice of toast with jam, 1 cup/240 mL of apple juice, and 1 cup/240 mL of coffee or tea (520 calories and 2 g fat). If vomiting occurs within 15 minutes after taking venetoclax and all expelled tablets are still intact, another dose may be taken. Otherwise, no replacement dose is to be taken. In cases where a dose of venetoclax is missed or forgotten, the patient should take the dose as soon as possible, ensuring that the dose is taken with food within 8 hours after the missed dose. Otherwise, the dose should not be taken. Patient compliance with the assigned daily dose of venetoclax will be assessed by standard pill counts. Bottles containing venetoclax tablets will be given to patients at regular scheduled visits. Previously distributed bottles will be returned to the clinic and tablets counted and returned study drug destroyed per institutional policy. Any discrepancy will be resolved with the patient at each clinic visit and documented in the patient record.

Any overdose or incorrect administration of Venetoclax and Quizartinib should be noted within Prometheus. Adverse events associated with an overdose or incorrect administration of study drug should be recorded as an Adverse Event within Prometheus.

- 5.1.1.1 Cycles may be started early (but not earlier than day 21) for patients with active disease if judged in the best interest of the patient.

*For the phase Ib, DLT defining period is 28 days. As such, cycle 2 should not be started before 28 days for the patients being treated on the phase Ib cohort to allow for adequate evaluation of DLTs.

- 5.1.1.2 Subsequent cycles may be delayed for recovery of toxicity or other medical conditions. Delays in start of subsequent cycles greater than 8 weeks will be acceptable only for patients who are deriving clinical benefit and after discussion with the principal investigator and the sponsor of potential risk/benefit ratio and complete documentation of the degree of clinical benefit and reason for continuation on this regimen.

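### The only hematologic DLT, prolonged myelosuppression at Day 42 or 8 weeks, falls outside the 28-day and one-cycle counts behind the MTD and Table 5

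*Combined protocol and SAP*

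**What the plan says.** **Definition.** Section 3.4 defines a DLT as a non-hematologic event of grade 3 or higher "occurring during the first cycle on study, with the following exceptions". Myelosuppression appears in the list that follows. Ordinary cytopenia does not count. Two prolonged forms do, both without leukemia:

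- "marrow cellularity < 5% with grade 4 neutropenia or thrombocytopenia on Day 42 or later from start of therapy"
- with a normocellular marrow, "8 weeks with grade 4 neutropenia or thrombocytopenia will be considered a DLT"

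**Window, phase Ib.** Section 3.1: "The DLT assessment period will be only during Cycle 1 of the Phase Ib (DLT assessment period = 28 days". Section 3.3: "The highest dose level at which 0-1/6 patients experience a DLT in the first 28 days of treatment will be the MTD". Section 5.1.1.1: "For the phase Ib, DLT defining period is 28 days". Section 11.1 repeats the 28-day limit in its MTD definition.

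**Window, phase II.** Section 11.2 monitors toxicity as DLT within one cycle and applies the Table 5 boundaries. The phase II report in 11.3 updates toxicity as of the end of the first 28 days.

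**Cycle length.** Section 5.1: "Patients will receive one cycle of therapy every 28 days (+/- 7 days".

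**The concern.** The MTD is a phase Ib primary objective, and Table 5 is the phase II toxicity stop. Section 3.4 says that prolonged myelosuppression is dose-limiting, yet both rules close before it can be diagnosed. A reader of the results would take the MTD and the Table 5 outcome to have accounted for prolonged marrow suppression when neither could register it.

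Overlapping marrow toxicity is foreseeable. Section 2.3.1 lists neutropenia and thrombocytopenia among the common venetoclax reactions, and section 2.2 names bone marrow as a principal toxicity target of quizartinib in animals. The count also sees little of the full combination. Under 5.5.4, venetoclax starts on Day 8 and reaches 400 mg on Day 11, so the 28 days contain 21 days of venetoclax, 18 of them at 400 mg.

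**Working it through.** **1. Window arithmetic**

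- Latest scheduled end of cycle 1: 28 + 7 = Day 35.
- Hypocellular limb: 42 - 28 = 14 days after the MTD cutoff, and 42 - 35 = 7 days after the longest scheduled cycle.
- Normocellular limb: 56 - 28 = 28 days and 56 - 35 = 21 days after. Section 3.4 does not say when the 8 weeks begin; they are counted here from the start of therapy.

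Both limbs fall outside both windows.

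**2. The plan's own figures**

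Table 5 stops when Pr(toxicity > 0.30) exceeds 0.90 under a Beta(0.6 + x, 1.4 + n - x) posterior.

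| n | Stop at x ≥ | Posterior at that x | Posterior at x - 1 |
|---|---|---|---|
| 5 | 4 | 0.975 | 0.875 |
| 10 | 6 | 0.963 | 0.880 |
| 15 | 8 | 0.960 | 0.893 |

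These match Table 5. An exact binomial recursion over the looks gives P(tox) for Table 5 and P(CRc) for Table 4. Combining them as 1 - (1 - P(tox))(1 - P(CRc)) reproduces all 25 cells of Table 6 to within 0.0001 (toxicity 0.30, CRc 0.50: 0.1605). The tables are correct; the issue is which events feed them.

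**3. What counting late events could change**

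The documents give no rate, so let l be the assumed share of patients without an early DLT who later meet the clause, with patients independent.

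- Cohort at 1/6 on Day 28, five patients left: P(at least 1 late) = 1 - (1 - l)^5. At l = 0.05: 1 - 0.95^5 = 0.226.
- Cohort at 0/6: P(at least 2 late of 6) = 1 - (1 - l)^6 - 6l(1 - l)^5. At l = 0.05: 1 - 0.735 - 0.232 = 0.033.
- Table 5, assuming a 15% early DLT rate: the recursion run at p = 0.15 + 0.85l.
- Implied share of remitters affected: l divided by a CRc rate of 50% (target) or 25% (historical), because only leukemia-free patients can qualify. Leukemia-free patients outside CRc would lower these shares somewhat.

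| l | 1/6 becomes ≥2/6 | 0/6 becomes ≥2/6 | Table 5 stop | Share of remitters |
|---|---|---|---|---|
| 0 (as written) | 0 | 0 | 0.35% | 0 |
| 2% | 9.6% | 0.6% | 0.6% | 4-8% |
| 5% | 22.6% | 3.3% | 1.1% | 10-20% |
| 10% | 41.0% | 11.4% | 2.8% | 20-40% |
| 20% | 67.2% | 34.5% | 11.2% | 40-80% |

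The last column shows why 10% and 20% are high-end assumptions.

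**The case against.** **The clause may carry its own clock.** It sits in a list of exceptions, so a specific item could override the general window. The escalation sentences in 3.3 also carry no day limit. However, 3.1 limits the assessment period to 28 days, 3.3 and 11.1 define the MTD by the first 28 days, and nothing holds a decision open or reopens a cleared dose.

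**Cycle 1 could run long.** Section 5.1.1.2 says "Subsequent cycles may be delayed for recovery of toxicity or other medical conditions", so one cycle in 11.2 might stretch past Day 42. This is a genuine ambiguity, which is why the point is limited to the schedule as written. The 28-day report in 11.3 cuts against it, and 5.2.1 plans no interruption for myelosuppression in the first 4 cycles.

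**Safeguards exist.** A reader might infer that late myelosuppression is ignored altogether. The documents do not support that. The Medical Monitor must approve each cohort advance (3.2). The RP2D may be set below the MTD after safety review (3.3, 3.5). Section 5.2.1 discontinues both drugs after more than 8 weeks of hypocellular cytopenia in certain responders. A hematologic DLT bars intra-patient escalation (5.2.3), and the study can be terminated (9.2). All of this stands, but none of it is a cohort-level count.

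**Counting would lower the wrong drug.** Section 5.2.3 regards neutropenia as likely due to venetoclax, and a reader might build the case on that. Table 1 holds venetoclax at 400 mg at every level, so de-escalation would lower only quizartinib. The objection stands against that argument. The case rests instead on whether the combination is tolerable at a given level.

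**Deleting the clause changes no decision.** This is true, and it bears on severity. The two rules would count what they count now, but the plan would say so.

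**Conclusion.** The conflict is real: section 3.4 intends prolonged myelosuppression to count, and on the written schedule it enters neither the 0-1/6 count nor Table 5. Should-fix.

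The size is unknown. At an assumed late rate of 2-5%, the MTD rule is most exposed where a cohort passes at 1/6 (10-23% would reach 2/6) and little exposed at 0/6 (0.6-3.3%). Table 5 barely moves: from 0.35% to 0.6-1.1% at an assumed 15% early DLT rate. These figures rest on the assumed rates and on independence between patients.

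Two stronger readings are tempting. One is that the selected MTD would be unsafe; without a late-event rate, the documents cannot show that. The other is that Tables 4-6 are miscalculated; they reproduce.

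**What to change.** **Preferred change**

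- Keep 28 days for non-hematologic DLTs.
- For leukemia-free patients with ongoing grade 4 neutropenia or thrombocytopenia at Day 28, extend the hematologic DLT window to Day 42, or Day 56 if the marrow is normocellular.
- Hold escalation or the MTD decision only when confirmed plus pending DLTs could reach 2 of 6. One confirmed plus one pending holds, as do two pending; none confirmed plus one pending does not.
- In phase II, update the Table 5 tally when status is known, under the hold strategy that 11.2 already applies to toxicity.
- State how pending patients who relapse or go to transplant before Day 42 or 56 are classified.
- State in 10.3 that hematologic values meeting the section 3.4 definition go on the CRF. It now excludes abnormal hematologic values, and its DLT exception is attached to chemistry values.

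**Cost.** Wording in 3.1, 3.3, 3.4, 5.1.1.1, 10.3, 11.1, 11.2 and 11.3, and an occasional wait of 2 weeks (42 - 28 = 14 days) to 4 weeks (56 - 28 = 28 days). Twice-weekly blood counts are already scheduled through cycle 3 (7.2.3). Pending patients would need a marrow outside the cycle 1 and cycle 3 schedule; 7.2.6 already allows this when counts call for it.

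**Alternative, wording only.** Remove the clause from the DLT definition, state that the MTD and Table 5 exclude prolonged myelosuppression, and define hematologic DLT separately for 5.2.3.
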